Histologic Remission (GS)	Subject-level	\leq 2B.0 (i.e., no increase in neutrophils in lamina propria [GS
	Ileal	destruction [GS 4.0], and no erosions, ulcerations or
	Colonic	granulation tissue [GS 5.0])
Histo-Endoscopic	Subject-level	Histologic response and endoscopic response (≥50%
Response (GS)		improvement from baseline in SES-CD score)
Histo-Endoscopic Remission (GS)	Subject-level	Histologic remission and endoscopic remission (SES-CD ≤ 4 and at least a 2-point reduction from baseline and no subscore greater than 1 in any individual component)
Histo-Endoscopic Remission (GS, Alternative Definition)	Subject-level	Histologic remission and endoscopic remission (SES-CD Score ≤2).

Robarts Histologic Index

Histological disease activity will be scored by a blinded experienced pathologist using the Robarts Histopathology Index (RHI). The RHI is a 4-item index (with 4 levels for each item) that evaluates chronic inflammation, lamina propria neutrophils, neutrophils in the epithelium, and erosion or ulceration as illustrated in Table 6. Total score ranges from 0 to 33, where higher scores denote more severe inflammation.

Table 6: Robarts Histologic Index

Component

- 1. Chronic inflammatory infiltrate
- 0=No increase
- 1=Mild but unequivocal increase
- 2=Moderate increase
- 3=Marked increase

2. Lamina propria neutrophils

- 0=None
- 1=Mild but unequivocal increase
- 2=Moderate increase
- 3=Marked increase

3. Neutrophils in epithelium

0=None

1=<5% crypts involved

2=<50% crypts involved

3=>50% crypts involved

4. Erosion or ulceration

0=No erosion, ulceration or granulation tissue

1=Recovering epithelium+adjacent inflammation

1=Probable erosion—focally stripped

2=Unequivocal erosion

3=Ulcer or granulation tissue

RHI = 1 x chronic inflammatory infiltrate level (4 levels)

+ 2 x lamina propria neutrophils (4 levels)

+ 3 x neutrophils in epithelium (4 levels)

+ 5 x erosion or ulceration (4 levels)

That is, RHI incorporates four components from the Geboes score (Grades 1, 2B, 3, and 5) into a weighted sum of the subgrades using the following formula,

RHI = 1*GS1 + 2*GS2B + 3*GS3 + 5*GS5

All components need to be scored with the re-parameterized grade score (Grade 5) to calculate the RHI.

If any of the components needed to calculate the RHI is missing, then the RHI will be set to missing.

All components need to be scored with the re-parameterized grade score (Grade 5) to calculate the RHI.

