- At each time point, all biopsies (up to 2 biopsies per region) obtained from each of the predefined anatomic regions will be scored separately for each of the 4 items:
- The single highest scoring item from each of the biopsies will be used as the score for that item.
- The weighted sum of the 4 scores within a region will be used as the Total score for that region (range 0-33). Furthermore,
 - The Ileal score will be equal to the Total Ileum Score
 - The worst scores for each item across the right colon, transverse colon, left colon, and rectum will be summed to obtain a Total Colonic Score.
 - The worst scores for each item across the 5 regions will be summed to obtain a Subject Score.

If both biopsies within a region are missing or unevaluable, the RHI will be missing for that region.

The definitions of baseline disease activity and histologic remission using RHI apply to a segment (region), Ileum, Colon, and Subject level. Histologic response, histo-endoscopic response, and histo-endoscopic remission will be evaluated on a subject level only.

Term	Scope	Definition			
Active Disease (RHI)	Subject-level	RHI with a score > 0 for any of Items 2-4 of RHI (lamina propria			
	Ileal	neutrophils, neutrophils in epithelium, or erosions or ulcerations)			
	Colonic				
Histologic Response (RHI)	Subject-level	\geq 50% reduction in RHI score from baseline or sub-scores of lamina propria neutrophils and neutrophils must be equal to 0, with no ulcers or erosions			
Histologic Remission	Subject-level	sub-scores of lamina propria neutrophils, neutrophils in the			
(RHI)	Ileal	epithelium and erosions or ulcerations must be equal to 0.			
	Colonic				
Histo-Endoscopic Response (RHI)	Subject-level	Histologic response and endoscopic response (≥50% improvement from baseline in SES-CD score)			
Histo-Endoscopic Remission (RHI)	Subject-level	Histologic remission and endoscopic remission (SES-CD ≤4 and at least a 2-point reduction from baseline and no subscore greater than 1 in any individual component)			
Histo-Endoscopic	Subject-level	Histologic remission and endoscopic remission (SES-CD Score			
Remission (RHI		≤2).			
Alternative Definition)					

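### As written, the SAP states no weights for the Colonic and Subject RHI scores, although it defines the RHI as a weighted index

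*SAP*

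**What the plan says.** SAP 5.5.1.5, under Robarts Histologic Index, describes the instrument this way: "The RHI is a 4-item index (with 4 levels for each item"). The range is given as "Total score ranges from 0 to 33, where higher scores denote more severe inflammation". The index is called a "weighted sum of the subgrades using the following formula", and the formula is "RHI = 1*GS1 + 2*GS2B + 3*GS3 + 5*GS5".

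The aggregation rules follow in one list:

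- **Region:** "The weighted sum of the 4 scores within a region will be used as the Total score for that region (range 0-33").
- **Ileum:** "The Ileal score will be equal to the Total Ileum Score".
- **Colon:** the worst item scores over the four colorectal segments, ending with "left colon, and rectum will be summed to obtain a Total Colonic Score".
- **Subject:** "The worst scores for each item across the 5 regions will be summed to obtain a Subject Score".

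The last two rules give neither weights nor a range. The table of terms at the end of the section defines RHI histologic response at subject level only. It requires either a reduction of at least 50% in RHI score from baseline, or zero scores on the neutrophil and erosion/ulceration items. SAP 5.5.2.10 lists change from baseline in the Colonic and Subject RHI scores, RHI response and RHI histo-endoscopic response at Weeks 12, 48 and 96.

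**The concern.** Within one list the SAP specifies a weighted sum at one level and a bare sum at the next two. No other place in the SAP or protocol applies the weights to the Colonic or Subject score. A programmer who follows those two rules to the letter produces a different index from the one defined just above them. Erosion or ulceration then counts no more than chronic infiltrate, and the Colonic and Subject scores sit on a different scale from the Ileal score.

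The likely source is the GHAS part of the same section. It uses almost the same sentence for its Subject score, and a plain sum is correct there because the GHAS has no weights.

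What is at stake is reproducibility. Two programmers could each claim to follow the SAP and report different change scores and different responders.

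**Working it through.** **Inputs (all SAP 5.5.1.5).** There are four items, each scored 0 to 3, in the order chronic infiltrate, lamina propria neutrophils, epithelial neutrophils, erosion/ulceration. The weights are 1, 2, 3 and 5. Active disease means any of items 2 to 4 above 0. Response is as defined above, including the all-zero branch.

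**1. Reproduce the stated range.**

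- Weighted maximum: 3 × (1 + 2 + 3 + 5) = 33, which matches the SAP.
- Plain-sum maximum: 3 + 3 + 3 + 3 = 12.

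Only the weighted sum gives 0 to 33. Erosion/ulceration supplies 15 of 33 points (45%) with weights and 3 of 12 (25%) without. Chronic infiltrate supplies 3 of 33 (9%) and 3 of 12 (25%).

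**2. Check coherence across levels.** Take ileal items (3,3,3,3) with every other region at 0. The Ileal score is 33. The worst items over the five regions are again (3,3,3,3), so the literal Subject score is 12. A score built from the worst item anywhere should not fall below the score of one of its own regions.

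**3. Check the GHAS parallel.** The eight GHAS features have maxima 2 + 2 + 2 + 2 + 3 + 1 + 1 + 3 = 16. This equals the range the SAP gives at every level, so the bare sum is right for that index.

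**4. Test the 50% rule at subject level.** Neither example meets the all-zero branch after baseline.

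| Baseline to post-baseline | Weighted | Plain sum |
|---|---|---|
| (2,2,2,3) to (2,2,2,0) | 2+4+6+15 = 27 to 2+4+6+0 = 12; fall 15/27 = 56%; response | 9 to 6; fall 3/9 = 33%; no response |
| (3,1,1,2) to (1,0,0,2) | 3+2+3+10 = 18 to 1+0+0+10 = 11; fall 7/18 = 39%; no response | 7 to 3; fall 4/7 = 57%; response |

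**5. Count how often the two sums disagree over possible profiles.** There are 4^4 = 256 item profiles. Four of them have items 2 to 4 all at 0, so 252 are active.

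- All pairs with an active baseline: 252 × 256 = 64,512. Responder status differs in 5,950 (9.2%): 3,704 respond only with weights and 2,246 only without.
- Pairs in which no item worsens: 10^4 − 10 = 9,990. Responder status differs in 1,615 (16.2%): 608 respond only with weights and 1,007 only without.

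The more common direction of disagreement changes between the two counts, so they give no basis for predicting a net bias.

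**The case against.** The strongest reply is that the SAP never says the sum is unweighted. It gives the weighted formula twice and states 0 to 33 for the RHI total without limiting that range to a region. The Ileal, Colonic and Subject rules hang under the bullet that introduces the weighted sum. The response definition refers to the RHI score, and the only RHI formula in the document is the weighted one. On that reading, the Colonic and Subject rules mean that the worst items are taken and the RHI is then formed from them. If the program does this, nothing changes.

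This stands as evidence of intent. A reader might infer from the bare wording that the sponsor chose to drop the weights, or that the analysis was run without them. The documents support neither inference: no such choice is recorded, and how the score was programmed is not shown. The reply does not make the rule correct as written. The list says weighted where it means weighted one level up and then omits it, and the literal result contradicts the index's own range.

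A second reply is that the profile counts are not effects. That is right. Each possible profile is counted once, and the documents give no distribution of histology scores from which a patient-level figure could be derived.

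**Conclusion.** The point holds as a defect of wording: the derivation is wrong as written, the intended one is almost certainly weighted, and the severity is minor. The literal rule yields 0 to 12 in place of 0 to 33 and can move a participant into or out of response. The 9.2% and 16.2% show that disagreement is not confined to odd corner cases. It would be tempting to read them as the share of patients misclassified, but they cannot carry that meaning. If the weights are in fact applied, the effect is zero.

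**Affected, if the rule is followed literally:** change from baseline in the Colonic and Subject RHI scores; the 50% branch of RHI histologic response; and, through it, RHI histo-endoscopic response. Each is assessed at Weeks 12, 48 and 96. Under SAP 5.5.3 all are exploratory with nominal p-values.

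**Not affected:**

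- RHI active disease, RHI remission, RHI histo-endoscopic remission and the all-zero branch of response, because these depend only on whether items are zero;
- the region and Ileal RHI scores, which are explicitly weighted;
- all GHAS and Geboes endpoints;
- every co-primary, secondary and multiplicity-controlled Week 48 endpoint.

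No confirmatory conclusion of the trial rests on this.

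**What to change.** In SAP 5.5.1.5, for both the Total Colonic and the Subject RHI score, replace the instruction that the worst item scores are summed with one that they are combined using the RHI weights 1, 2, 3 and 5, giving a range of 0 to 33. Leave the GHAS wording alone. Then confirm that the derivation program applies the weights at both levels. Two quick tests are enough: a participant with all four ileal items at 3 must have a Subject score of 33, and no Subject score may be lower than the same participant's Ileal score.

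The cost is one phrase in two bullets and a programming check. No new data, design change or change to the testing procedure is needed. If the check shows that a plain sum was used, rerun the affected exploratory outputs listed in the verdict.

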5.5.2. List of Exploratory Endpoints

In addition to the primary and secondary endpoints, exploratory endpoints related to disease status, HRQOL outcomes, inflammatory biomarkers, and health economics will be analyzed.

5.5.2.1. CDAI based endpoints

- Change in CDAI score from baseline over time
- Clinical remission over time
- Clinical remission at both Week 12 and Week 24
- Clinical remission at both Week 12 and Week 48 (Sustained remission)
- Clinical response over time
- Clinical response at both Week 12 and Week 24
- Clinical response at both Week 12 and Week 48 (Sustained response)
- Durable clinical remission at Week 48 (CDAI <150 for ≥80% of all visits between Week 12 and Week 48 [ie, at least 8 of 10 visits]), which must include Week 48)
- Change from baseline in the weighted CDAI component scores over time

5.5.2.2. Corticosteroid related endpoints

- Corticosteroid-free clinical remission at Week 24
- Corticosteroid-free clinical remission at Week 48
- 90-day corticosteroid-free clinical remission at Week 48
- Average daily prednisone-equivalent (P.Eq) corticosteroid dose (excluding budesonide and beclomethasone dipropionate) over time in participants who were receiving corticosteroids other than budesonide and beclomethasone dipropionate at baseline
- Change from baseline in the average daily prednisone equivalent (P.Eq) oral corticosteroids dose (mg/day; excluding budesonide and beclomethasone dipropionate) at each visit over time in participants who were receiving oral corticosteroids other than budesonide and beclomethasone dipropionate at baseline
- Number of participants who were not receiving concomitant corticosteroids at Weeks 24, 48, 96 in participants who were receiving concomitant corticosteroids at baseline
- Number of participants who were not receiving corticosteroids for at least 90 days prior to Weeks 48, 96 in participants who were receiving concomitant corticosteroids at baseline

5.5.2.3. PRO-2 remission

- PRO-2 remission over time
- Corticosteroid-free PRO-2 remission at Week 48 (defined as $AP \le 1$ and $SF \le 3$, and no worsening of AP or SF from baseline, and not receiving corticosteroids at Week 48)
- Durable PRO-2 remission at Week 48 (defined as AP ≤1 and SF ≤3, and no worsening of AP or SF from baseline, for ≥80% of all visits between Week 12 and Week 48 [ie, at least 8 of 10 visits], which must include Week 48)

5.5.2.4. Abdominal Pain and Stool Frequency

- AP score (daily average based on the CDAI assessment) ≤1 over time, among participants with daily average AP score >1 at baseline
- Number of liquid or very soft stools (daily average based on the CDAI assessment) ≤ 3 over time, among participants with daily average number of liquid or very soft stools >3 at baseline
- Absence and/or resolution of abdominal pain (defined as a mean daily CDAI AP score of 0 in the week prior to the visit) among participants with mean AP>1 at baseline, over time
- SF remission (defined as number of liquid or very soft stools daily average based on CDAI assessment SF ≤ 1.5 in the week prior to the visit) among participants with mean SF >2.5 at baseline, over time

5.5.2.5. Endoscopy

- Change in SES-CD score from baseline at Week 12, Week 48, and Week 96
- Endoscopic response at Week 48 and Week 96
- Endoscopic response (Alternative Definition) at Week 12, Week 48, and Week 96

- Endoscopic remission at Week 12, Week 48, and Week 96
- Endoscopic remission (Alternative Definition) at Week 12, Week 48, and Week 96
- Endoscopic response at both Weeks 12 and 48 (sustained endoscopic response)
- Endoscopic response at Week 12 and endoscopic remission at Week 48
- Endoscopic response at Week 48 and CRP concentration ≤5 mg/L at Week 48 among participants with elevated CRP (>5 mg/L) at baseline
- Endoscopic response at Week 48 and fecal calprotectin concentration $\leq 250 \ \mu g/g$ at Week 48 among participants with elevated fecal calprotectin $\geq 250 \ \mu g/g$ at baseline.
- Clinical remission at Week 12 and endoscopic response at Week 12
- Clinical remission at Week 48 and endoscopic response at Week 48
- Deep remission at Week 48
- Endoscopic healing at Week 12, Week 48, and Week 96

5.5.2.6. Fistula

- Fistula response over time, defined as a ≥50% reduction from baseline in the number of draining fistulas, among participants with 1 or more fistulas at baseline
- Complete fistula response over time, among participants with 1 or more fistulas at baseline

5.5.2.7. Biomarkers

- Clinical response and ≥50% reduction from baseline in CRP or fecal calprotectin at Week 12, Week 24, and Week 48
- Clinical remission and ≥50% reduction from baseline in CRP or fecal calprotectin at Week 12, Week 24, and Week 48
- Change in CRP over time
- CRP concentrations ≤5 mg/L over time among participants with elevated CRP (>5 mg/L) at baseline
- Change in fecal calprotectin from baseline over time
- Fecal calprotectin concentration ≤250 µg/g over time, among participants with fecal calprotectin >250 µg/g at baseline
- Fecal calprotectin concentration $\leq 100 \ \mu g/g$ over time, among participants with fecal calprotectin >250 $\mu g/g$ at baseline
- Fecal calprotectin concentration \leq 50 µg/g over time, among participants with fecal calprotectin >250 µg/g at baseline
- Clinical remission and CRP concentration ≤5 mg/L at Week 24 and Week 48, among participants with elevated CRP at baseline
- Clinical remission and fecal calprotectin concentration $\leq 250 \ \mu g/g$ at Week 24 and Week 48, among participants with elevated fecal calprotectin (>250 $\mu g/g$) at baseline

- Statistical Analysis Plan Amendment 1 CNTO1959CRD3004
- Clinical response and CRP concentration ≤5 mg/L at Week 24 and Week 48, among participants with elevated CRP at baseline
- Clinical response and fecal calprotectin concentration $\leq 250 \ \mu g/g$ at Week 24 and Week 48, among participants with elevated fecal calprotectin (>250 $\mu g/g$) at baseline
- Clinical response and CRP concentration ≤5 mg/L or fecal calprotectin concentration ≤250 µg/g over time, among participants with elevated CRP and fecal calprotectin >250 µg/g at baseline
- Clinical remission and CRP concentration ≤5 mg/L or fecal calprotectin concentration ≤250 μg/g over time, among participants with elevated CRP and fecal calprotectin >250 μg/g at baseline

5.5.2.8. IBDQ and PROMIS-29

- Change from baseline in total IBDQ score and domain scores over time
- IBDQ remission (IBDQ \geq 170) over time
- IBDQ response (≥16-point improvement from baseline) over time
- Change from baseline in the 7 PROMIS-29 domains over time
- Change from baseline in the pain NRS score of PROMIS-29 over time
- Responses in the 7 PROMIS-29 domains (improvement of ≥5, ≥7 and ≥9 points from baseline) over time
- Responses in the pain NRS score of PROMIS-29 (improvement of ≥3 points from baseline) over time
- Change from baseline in the PROMIS-29 PCS and MCS over time
- Responses in the PROMIS-29 PCS and MCS (improvement of ≥5, ≥7, and ≥9 points from baseline) over time

5.5.2.9. BSFS and AP-NRS

- Change from baseline in average daily number of BSFS types 6 and 7 stools over time through Week 48.
- A ≥2 reduction in average daily number of BSFS types 6 and 7 stools over time through Week 48.
- Change in abdominal pain NRS (daily average based on a 0-10 NRS) from baseline over time through Week 48.
- A 3-point reduction in abdominal pain NRS (daily average based on a 0-10 NRS) from baseline over time through Week 48, among participants with pain NRS score ≥3 at baseline.

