5.1. Inclusion Criteria

Each potential participant must satisfy all of the following criteria to be enrolled in the study:

1. Man or woman (according to their reproductive organs and functions assigned by chromosomal complement) of ≥ 18 years of age (or the legal age of consent in the jurisdiction in which the study is taking place).

- 2. Have Crohn's disease or fistulizing Crohn's disease of at least 3 months duration (defined as a minimum of 12 weeks), with colitis, ileitis, or ileocolitis, confirmed at any time in the past by radiography, histology, and/or endoscopy.
- 3. Have clinically active Crohn's disease, defined as a baseline CDAI score ≥220 but ≤450 and either:
 - a. Mean daily SF count ≥4, based on the unweighted CDAI component of the number of liquid or very soft stools

OR

- b. Mean daily AP score ≥ 2 , based on the unweighted CDAI component of AP
- 4. Have endoscopic evidence of active ileocolonic Crohn's disease as assessed by central endoscopy reading at the screening endoscopy (SoA [Section 1.3]) defined as a screening SES-CD score ≥6 (or ≥4 for participants with isolated ileal disease), based on the presence of ulceration in at least 1 of the 5 ileocolonic segments, resulting in the following specified ulceration component scores:
 - a. A minimum score of 1 for the component of "size of ulcers"

AND

- b. A minimum score of 1 for the component of "ulcerated surface"
- 5. A participant who has had extensive colitis for ≥ 8 years, or disease limited to a segment of the colon for ≥ 10 years, must:
 - a. Have had a full colonoscopy to assess for the presence of dysplasia within 1 year before the first dose of study intervention

OR

b. Have a full colonoscopy with biopsy surveillance for dysplasia as the baseline endoscopy during the screening period. Results from these surveillance biopsies must be negative for dysplasia (low-grade, high-grade, or "indefinite dysplasia in reactive atypia") prior to the first dose of study intervention

Concomitant or Previous Medical Therapies Received

- 6. Prior or current medication for Crohn's disease must include at least 1 of the following, and must fulfill additional criteria as described in Appendix 2 (Section 10.2) and Appendix 3 (Section 10.3) as applicable:
 - a. Current treatment with oral corticosteroids (including budesonide and beclomethasone dipropionate) and/or immunomodulators (AZA, 6-MP, MTX)

OR

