1.2. Study Design

An overview of the study design is provided in Figure 1.

Target Population

The target population is adult participants with moderately to severely active Crohn's disease (of at least 3 months duration) with colitis, ileitis, or ileocolitis previously confirmed by radiography, histology, and/or endoscopy. To be eligible for the study, participants must also have endoscopic evidence of active Crohn's disease and have demonstrated an inadequate response or failure to tolerate previous conventional or biologic therapy.

Figure 1: Schematic Overview of the Study

Active Disease Criteria

At baseline, participants must have active Crohn's disease, defined as follows:

1. Clinically active Crohn's disease

a. CDAI score \geq 220 but \leq 450

AND

- b. Having active symptoms defined as EITHER
 - Mean daily Stool Frequency (SF) count ≥4, based on the unweighted CDAI component of the number of liquid or very soft stools

OR

 Mean daily Abdominal Pain (AP) score ≥2, based on the unweighted CDAI component of AP

AND

2. Endoscopic evidence of ileocolonic Crohn's disease

A SES-CD score ≥ 6 (or ≥ 4 for participants with isolated ileal disease), as assessed by central endoscopy reading at the screening endoscopy, based on the presence of ulceration in at least 1 of the 5 ileocolonic segments, resulting in the following specified ulceration component scores:

a. a minimum score of 1 for the component of "size of ulcers"

AND

b. a minimum score of 1 for the component of "ulcerated surface".

Medication History Criteria

The two groups based on prior therapies comprising the target population are briefly described below.

Conventional therapy failure or intolerance (CON-Failure)

- Participants must have demonstrated an inadequate response to, or have failed to tolerate, at least 1 of the following conventional Crohn's disease therapies: oral corticosteroids (including prednisone, budesonide, and beclomethasone dipropionate) or the immunomodulators azathioprine (AZA), 6-mercaptopurine (6-MP) or methotrexate (MTX).
- Participants who have demonstrated corticosteroid dependence (ie, an inability to successfully taper corticosteroids without a return of the symptoms of Crohn's disease) are also eligible.

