Type 1: Separate hard lumps, like nuts (difficult to pass) Type 2: Sausage-shaped, but lumpy Type 3: Like a sausage but with cracks on its surface Type 4: Like a sausage or snake, smooth and soft (average stool) Type 5: Soft blobs with clear cut edges Type 6: Fluffy pieces with ragged edges, a mushy stool (diarrhoea) Type 7: Watery, no solid pieces, entirely liquid (diarrhoea)

Average number of BSFS types 6 and 7 stools per day is defined as the sum of number of BSFS types 6 and 7 stools in previous 7 days in a dairy card divided by the total number of days assessments were performed. Similarly, average number of BSFS types 5, 6 and 7 stools per day is defined as the sum of number of BSFS types 5, 6 and 7 stools in previous 7 days in a dairy card divided by the total number of days assessments were performed.

Average number of BSFS stools per day at a scheduled visit will not be calculated if total days of assessment is less than 5 within the previous 7 days prior to a scheduled visit.

PRO-2 Remission

PRO-2 remission is defined as AP mean daily score at or below 1 (AP \leq 1) AND an SF mean daily score at or below 3 (SF \leq 3), and no worsening of AP or SF from baseline.

Corticosteroid-free Clinical Remission

Corticosteroid-free clinical remission is defined as CDAI score <150 and not receiving corticosteroids (at a specified visit).

90-day Corticosteroid-free Clinical Remission

90-day corticosteroid-free clinical remission is defined as achieving clinical remission and not receiving corticosteroids for 90 days prior to the specified visit e.g. 90-day corticosteroid-free clinical remission at Week 48 is defined as CDAI score <150 at Week 48 and not receiving corticosteroids for 90 days prior to Week 48.

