5.7.7. Definition of Subgroups

When the number of participants in each subgroup permits, the consistency of treatment effect for the co-primary endpoints will be evaluated for the subgroups listed below using the co-primary estimands.

The following subgroups will be evaluated for the co-primary endpoints in this study:

1. Demographics:

- a. Age (\leq median age, > median age), Age (<65 years old, \geq 65 years old)
- b. Sex (male, female)
- c. Race (white, non-white), Race (White, Black or African American, Asian, Other)
- d. Ethnicity (Hispanic or Latino, not Hispanic or Latino)
- e. Weight at baseline (quartiles)
- f. Region (Asia, Eastern Europe, North America, Rest of World)

2. Baseline disease characteristics:

- a. Crohn's disease duration (≤ 5 years, > 5 years to ≤ 15 years, or > 15 years)
- b. Involved gastrointestinal areas based on central reader assessment (ileum only, colon only, ileum & colon)
- c. CDAI score ($\leq 300, >300$)
- d. CRP ($\leq 5 \text{ mg/L}$, > 5 mg/L)
- e. Fecal calprotectin ($\leq 250 \ \mu g/g$, $> 250 \ \mu g/g$)
- f. SES-CD ($\leq 12, > 12$)
- g. $SF \ge 4$ only, $AP \ge 2$ only, both $SF \ge 4$ and $AP \ge 2$

3. Concomitant medication use at baseline:

- a. Oral 5-ASA compounds (receiving, not receiving)
- b. Oral corticosteroids including budesonide and beclomethasone dipropionate (receiving, not receiving)
- c. 6-MP/AZA/MTX (receiving, not receiving)
- d. Oral corticosteroids and (6-MP/AZA/MTX) (receiving, not receiving)
- e. Oral corticosteroids or (6-MP/AZA/MTX) (receiving, not receiving)

4. CD-related Medication History:

- a. Refractory or intolerant to 6-MP/AZA/MTX (yes, no)
- b. Refractory, dependent or intolerant to oral or IV corticosteroids (yes, no)
- c. Refractory, dependent, or intolerant to oral or IV corticosteroids, but not refractory or intolerant to 6-MP/AZA/MTX (yes, no)
- d. Refractory, dependent or intolerant to oral or IV corticosteroids, and refractory or intolerant to 6-MP/AZA/MTX (yes, no)
- e. BIO-failure status
 - BIO-Failure (Bio-failure status = yes)
 - CON-Failure (Bio-failure status = no)
 - i. Bio-naïve
 - ii. Bio-experienced [but not documented failure]
- f. Participants with biologic failure
 - Primary nonresponse, secondary nonresponse, or intolerance to
 - At least one anti-TNF (yes, no)
 - Two or more anti-TNFs
 - Anti-TNF only (yes, no)
 - Vedolizumab (yes, no)
 - Vedolizumab and at least one anti-TNF (yes, no)

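### The BSFS responder endpoint keeps participants who start below 2 loose stools per day and so cannot respond; the result is valid but diluted, and a baseline condition like the one on AP-NRS would sharpen it

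*SAP*

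**What the plan says.** SAP 5.5.2.9 lists two responder endpoints side by side, both followed through Week 48.

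- **BSFS:** an at-least-2 "reduction in average daily number of BSFS types 6 and 7 stools", with no condition on the baseline value.
- **AP-NRS:** a 3-point reduction, but only "among participants with pain NRS score ≥3 at baseline".

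The BSFS score is a daily average of a count. SAP 5.5.1.1 begins its definition with "Average number of BSFS types 6 and 7 stools per day is defined as the sum", taken over the previous 7 days and divided by the number of days assessed.

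SAP 5.5.2.4 also conditions its symptom endpoints on baseline. One stool endpoint, for example, is evaluated "among participants with daily average number of liquid or very soft stools >3 at baseline".

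SAP Section 4 makes the Full Analysis Set the default for efficacy. SAP 5.5.3 sends binary exploratory endpoints to the method used for the secondary endpoints, which is the Mantel-Haenszel common risk difference (SAP 5.4.3.1).

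On entry, SAP 1.2 introduces the symptom requirement with "Having active symptoms defined as EITHER", followed by a mean daily stool count of at least 4 or a mean daily pain score of at least 2. The pain arm in Protocol 5.1, criterion 3b, is "based on the unweighted CDAI component of AP" and carries no stool requirement. SAP 5.7.7 plans a subgroup of participants who meet the pain threshold only.

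**The concern.** A participant who qualifies on pain may have few or no type 6 and 7 stools at baseline. If the baseline average is below 2, a fall of 2 is impossible whatever the treatment does, yet that participant stays in the denominator.

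On the absolute scale that the SAP uses, such participants pull both response rates and their difference toward zero. They carry no information about treatment. Because the AP-NRS endpoint beside it admits only people with room to improve by the required amount, the two responder rates also rest on different kinds of denominator.

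What is at stake is the size and sensitivity of one exploratory result.

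**Working it through.** **Figures in the plan.** The documents state no rate, sample size or power for this endpoint, so there is no figure of its own to reproduce. As a check on the inputs, a 2-sided 0.05 chi-square calculation with 212 versus 106 reproduces SAP Table 1: 91% for 10% vs 25%, 94% for 13% vs 30%, and above 99% for 13% vs 35%.

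**Step 1: can an eligible participant start below 2?** Use the CDAI weights in Protocol Appendix 8 and the entry range 220 to 450. Components not listed contribute 0.

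- No loose stools, pain 3 per day, well-being 3 per day: 5 × 21 + 7 × 21 = 105 + 147 = 252. Eligible on CDAI and on pain.
- 1.9 loose stools per day, pain 2, well-being 2, hematocrit 6 points below standard: 2 × 13.3 + 5 × 14 + 7 × 14 + 6 × 6 = 26.6 + 70 + 98 + 36 = 230.6. Also eligible.

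So it can happen. This does not show how often. The CDAI stool item (liquid or very soft stools) is also only a proxy for BSFS types 6 and 7.

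**Step 2: size of the dilution.** Let f be the share with baseline below 2, equal across arms in expectation because it is fixed before randomization. Let p_G and p_P be the response rates among those able to respond.

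- All participants: p_G(1 − f) − p_P(1 − f) = (1 − f)(p_G − p_P).
- Restricted to baseline ≥2: p_G − p_P.
- The risk ratio p_G/p_P is the same in both.

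**Step 3: sensitivity.** With n_G and n_P participants and unpooled variances, the squared test statistics are:

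- all participants: (1 − f)(p_G − p_P)² ÷ [p_G(1 − p_G(1 − f))/n_G + p_P(1 − p_P(1 − f))/n_P]
- restricted: (1 − f)(p_G − p_P)² ÷ [p_G(1 − p_G)/n_G + p_P(1 − p_P)/n_P]

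The numerators are equal. The restricted denominator is smaller for any f above 0, so restricting raises the expected z even though it uses fewer participants.

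**Step 4: numbers.** Assumptions, none from the documents: p_G = 50%, p_P = 30%, f from 5% to 40%. Sample sizes follow Protocol Section 3: at Week 12 the combined guselkumab group is compared with placebo (212 vs 106), and after Week 12 each guselkumab group is compared with placebo (106 vs 106).

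| f | Difference, all | Difference, restricted | z at 212 vs 106: all → restricted | z at 106 vs 106: all → restricted |
|---|---|---|---|---|
| 5% | 19 points | 20 points | 3.41 → 3.47 | 2.91 → 2.96 |
| 10% | 18 | 20 | 3.27 → 3.38 | 2.78 → 2.88 |
| 20% | 16 | 20 | 3.00 → 3.18 | 2.53 → 2.72 |
| 40% | 12 | 20 | 2.46 → 2.76 | 2.07 → 2.35 |

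Worked line for f = 20% at 212 vs 106:

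- All: 0.16 ÷ √(0.40 × 0.60/212 + 0.24 × 0.76/106) = 0.16 ÷ 0.0534 = 3.00.
- Restricted: 0.20 ÷ √(0.25/169.6 + 0.21/84.8) = 0.20 ÷ 0.0629 = 3.18.

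In power terms (pooled chi-square, 212 vs 106), restricting moves 88.6% to 90.7% at f = 10% and 82.1% to 87.0% at f = 20%. At 106 vs 106 and f = 20% it moves 70.7% to 76.2%. These are unstratified approximations to the stratified test in the SAP.

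**The case against.** The strongest reply is that nothing is wrong with the estimate. The all-participant risk difference answers a proper question: what share of trial participants lost at least 2 such stools per day? Restricting changes the population and therefore the question. Type I error is not inflated, the risk ratio is unchanged, and the effect is conservative. All of that stands. A reader might infer that the planned analysis is biased or understates the treatment effect. The documents do not support that, because the Full Analysis Set is the declared default and the floor share is balanced by randomization.

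Second, a baseline condition is not a uniform convention in this SAP. In 5.5.2.8 the IBDQ response, the PROMIS-29 domain responses and the PROMIS-29 pain NRS response (at least 3 points on a 0 to 10 scale) have none, and the last has the same kind of floor. This stands too. It argues for looking at that endpoint as well, and it does not make certain non-responders informative here.

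Third, related results already exist: the two baseline-restricted stool frequency endpoints in 5.5.2.4 and the BSFS change from baseline in everyone. They soften the loss, but the 5.5.2.4 endpoints use the CDAI stool count and different thresholds.

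Fourth, the floor share may be small. Entry on pain alone implies a stool count below 4, not below 2, and such participants must still reach a CDAI of 220 largely from other components. A share of 20% or 40% is illustrative, and reading it as what this trial will see goes beyond the documents.

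**Conclusion.** The point holds as a modest improvement to one exploratory endpoint. Participants starting below 2 can be enrolled, cannot respond, and remain in the denominator. The reported difference is then (1 − f) times that among participants able to respond, and the expected test statistic is lower than in the restricted set for any f above 0.

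The direction and the factor (1 − f) follow from the definitions. The amounts depend on assumed rates of 50% versus 30% and on an unknown f: a loss of 1 to 2 points at 5% to 10%, 4 points at 20% and 8 at 40%. Every illustrated z stays above 1.96 with or without the restriction.

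A reader might take this to touch the trial's main findings. It does not: the endpoint lies outside the testing sequence in SAP 5.4.3.2 and 5.5.3 and its p-values are nominal. Nor do the documents plan any comparison between the BSFS and AP-NRS responder rates, so the differing denominators matter only to someone reading the two side by side.

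**What to change.** In SAP 5.5.2.9, limit the at-least-2 BSFS responder endpoint to participants whose baseline average is at least 2 type 6 and 7 stools per day, matching the way the AP-NRS line is written. If the all-participant rate is wanted, report both and state the number below 2 at baseline in each arm. Keep the BSFS change-from-baseline endpoint in all participants. Consider the same condition (baseline of at least 3) for the PROMIS-29 pain NRS response in 5.5.2.8.

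The cost is one phrase or one extra display. The baseline BSFS score is already needed for the existing endpoint, so no new data are required. The downside is a smaller denominator and a narrower population for one exploratory result.
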